3.11 Pharmacokinetic Analysis

A population PK analysis will be used to describe the PK of entinostat. The effects of

patient factors (e.g., demographics, clinical chemistries, and disease) on entinostat PK will be evaluated. In addition, the relationship between entinostat exposure parameters and indicators of safety will be assessed. Descriptive statistics will be used to summarize the PK of pembrolizumab and anti-pembrolizumab antibodies at each cycle and time point.

Specific details for these analyses as well as analyses of trough pembrolizumab levels and anti-pembrolizumab antibodies will be provided in a separate analysis plan.

3.12 Immune Correlate Analysis

Immune correlate values will be summarized in a descriptive manner. For immune correlates measured on a continuous scale, the number of patients with non-missing data, mean, standard error or standard deviation, median, 25th percentile (first quartile), 75th percentile (third quartile), minimum, and maximum values will be presented. For discrete data, the frequency and percent distribution will be presented. The Wilcoxon signed rank test (for within-treatment comparisons) and Wilcoxon rank sum test (for between-treatment comparisons) will be used to identify any systematic changes in biomarker levels from baseline. Additionally, the correlation among the various initial immune correlate values may be assessed by calculating Spearman's correlation coefficient. Analysis of covariance models may be used to explore the relationship between changes in immune correlates and selected measures of antineoplastic activity (e.g., maximum change from baseline in the sum of product diameters in measurable lesions).

5 APPENDIX

5.1 Laboratory Test Groupings and Standard Normal Range

Analyte	Standard Unit	Significant Digits	Directional Change of Interest	Standard Normal Range [†]
Lab group = Hematology, WBC with Differential				
WBC count [‡]	10 ⁹ cells/L	XX.X	Decrease	3.2 – 9.8
Basophil count	10 ⁶ cells/L	XX	Decrease	15 – 50
Eosinophil count	10 ⁶ cells/L	XXX	Decrease	50 – 250
Lymphocyte count [‡]	10 ⁶ cells/L	XXXX	Decrease	1500 – 3000
Monocyte count	10 ⁶ cells/L	XXX	Decrease	285 – 500
Neutrophil count [‡]	10 ⁶ cells/L	XXXX	Decrease	3000 – 5800
Lab group = Hematology, Erythrocytes and Platelets				
Hematocrit	Fraction of 1.00	0.XX	Decrease	0.33 – 0.43 (female)
				0.39 – 0.49 (male)
Hemoglobin [‡]	g/L	XXX	Decrease	115 – 155 (female)
				140 – 180 (male)
RBC count	10 ¹² /L	X.X	Decrease	3.5 – 5.0
Platelet count [‡]	10 ⁹ /L	XXX	Decrease	130 – 400
Lab group = Hematology, Coagulation				
PT	seconds	XX	Increase	9 – 12
PTT [‡]	seconds	XX	Increase	22 – 37

[†] Standard normal ranges are provided for reference and not will be used in analysis unless laboratory normal ranges are missing. Source: Laposta, M: *SI Unit Conversion Guide*, The New England Journal of Medicine Books, Boston, 1992.

[‡] If present, indicates CTCAE toxicity grade is defined for the analyte.

Laboratory Test Groupings and Standard Normal Range (continued)

Analyte	Standard Unit	Significant Digits	Directional Change of Interest	Standard Normal Range [†]
Lab group = Chemistry, Hepatic				
Albumin [‡]	g/L	XX	Decrease	40 – 60
Alk Phos [‡]	U/L	XXX	Increase	30 – 120
ALT [‡]	U/L	XXX	Increase	0 – 35
AST [‡]	U/L	XXX	Increase	0 – 35
Lactic dehydrogenase	U/L	XXX	Increase	50 – 150
Total Bilirubin [‡]	micromol/L	XX	Increase	2 – 18
Total Protein	g/L	X.XX	Decrease	60 – 80
Lab group = Chemistry, Renal				
BUN	mmol/L of urea	X.X	Increase	3.0 – 6.5
Creatinine [‡]	micromol/L	XXX	Increase	50 – 110
Creatinine clearance	mL/min	XXX	Decrease	75 – 125

[†] Standard normal ranges are provided for reference and not will be used in analysis unless laboratory normal ranges are missing.

Source: Laposta, M: *SI Unit Conversion Guide*, The New England Journal of Medicine Books, Boston, 1992.

[‡] If present, indicates CTCAE toxicity grade is defined for the analyte.

Laboratory Test Groupings and Standard Normal Range (continued)

Analyte	Standard Unit	Significant Digits	Directional Change of Interest	Standard Normal Range [†]
Lab group = Chemistry, Electrolytes				
Bicarbonate [‡]	mmol/L	XX	Both	22 – 28
Calcium [‡]	mmol/L	X.XX	Both	2.20 – 2.56
Chloride	mmol/L	XXX	Both	95 – 105
Magnesium [‡]	mmol/L	X.XX	Both	0.80 – 1.20
Phosphorus	mmol/L	X.XX	Both	0.80 – 1.60
Potassium [‡]	mmol/L	X.X	Both	3.5 – 5.0
Sodium [‡]	mmol/L	XXX	Both	135 – 147
Lab group = Chemistry, Metabolic				
Glucose [‡]	mmol/L	XX.X	Both	3.9 – 6.1
Uric Acid	micromol/L	XXX	Increase	120 – 420

[†] Standard normal ranges are provided for reference and not will be used in analysis unless laboratory normal ranges are missing.

Source: Laposta, M: *SI Unit Conversion Guide*, The New England Journal of Medicine Books, Boston, 1992.

[‡] If present, indicates CTCAE toxicity grade is defined for the analyte.

5.2 CTCAE Toxicity Grades: Hematology

Analyte	Standard Unit	Directional Change of Interest	Toxicity Grades (CTCAE v4.03)
WBC with Differential			
WBC count	$10^9/\text{L}$	Decrease	Grade 0: $\geq \text{LLN}$ Grade 1: $< \text{LLN} - 3.0 \times 10^9/\text{L}$ Grade 2: $< 3.0 - 2.0 \times 10^9/\text{L}$ Grade 3: $< 2.0 - 1.0 \times 10^9/\text{L}$ Grade 4: $< 1.0 \times 10^9/\text{L}$
Lymphocyte count	10^6 cells/L	Decrease	Grade 0: $\geq \text{LLN}$ Grade 1: $< \text{LLN} - 0.8 \times 10^6/\text{L}$ Grade 2: $< 0.8 - 0.5 \times 10^6/\text{L}$ Grade 3: $< 0.5 - 0.2 \times 10^6/\text{L}$ Grade 4: $< 0.2 \times 10^6/\text{L}$
Neutrophil count	10^6 cells/L	Decrease	Grade 0: $\geq \text{LLN}$ Grade 1: $< \text{LLN} - 1.5 \times 10^6/\text{L}$ Grade 2: $< 1.5 - 1.0 \times 10^6/\text{L}$ Grade 3: $< 1.0 - 0.5 \times 10^6/\text{L}$ Grade 4: $< 0.5 \times 10^6/\text{L}$

LLN=lower limit of normal. ULN=upper limit of normal. The LLN and ULN for each analyte will be determined from the normal range of each local laboratory.

CTCAE Toxicity Grades: Hematology (continued)

Analyte	Standard Unit	Directional Change of Interest	Toxicity Grades (CTCAE v4.03)
Erythrocytes and Platelets			
Hemoglobin	g/L	Decrease	Grade 0: \geq LLN Grade 1: $<$ LLN – 100 g/L Grade 2: $<$ 100 – 80 g/L Grade 3: $<$ 80 g/L Grade 4: Not defined
Platelet count	$10^9/L$	Decrease	Grade 0: \geq LLN Grade 1: $<$ LLN – $75 \times 10^9/L$ Grade 2: $<$ $75 - 50 \times 10^9/L$ Grade 3: $<$ $50 - 25 \times 10^9/L$ Grade 4: $<$ $25 \times 10^9/L$
Coagulation			
PTT	seconds	Increase	Grade 0: \leq ULN Grade 1: $>$ ULN – $1.5 \times$ ULN Grade 2: $>$ $1.5 - 2.5 \times$ ULN Grade 3: $>$ $2.5 \times$ ULN Grade 4: Not defined

LLN=lower limit of normal. ULN=upper limit of normal. The LLN and ULN for each analyte will be determined from the normal range of each local laboratory.

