3.10.2 Laboratory Evaluations

Hematology and serum chemistries will be summarized using summary statistics for the following values by cohort ~~and overall~~: baseline value, minimum and maximum post-baseline values, average post-baseline value, and last post-baseline value. Change

from baseline for each of these post-baseline values will also be summarized.

Whenever available, laboratory values will be assigned toxicity grades using the NCI-CTCAE, version 4.03. Shifts in laboratory values to outside the local laboratory normal range will be evaluated for selected laboratory tests by assessing, relative to the baseline value, the maximum increase and/or decrease observed throughout the course of study treatment, and the last reported value. The number and proportion of patients with directional shifts above or below the normal range will be summarized for selected laboratory tests. Similar analyses will be performed for shifts in NCI CTCAE toxicity grades relative to the baseline toxicity grade.

Percentages will be based on the total number of patients with a baseline assessment and at least one post-baseline assessment for the given laboratory parameter. Laboratory test groupings and standard normal ranges are described in Appendix 5.1, and CTCAE toxicity grades for hematology and chemistry parameters are described in Appendix 5.2 and Appendix 5.3, respectively.

Listings of all clinical laboratory data for each patient will be provided. A separate listing of all out of normal range as well as all toxicity grade values will also be provided.

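### SAP Appendix 5.2 sets the neutrophil and lymphocyte grade limits 1000 times too low, so severe falls would be tabulated as Grade 1 if programmed as written

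*SAP*

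**What the plan says.** SAP 3.10.2 gives the general rule, "Whenever available, laboratory values will be assigned toxicity grades using the NCI-CTCAE, version 4.03", and then says where the hematology limits are set out: "CTCAE toxicity grades for hematology and chemistry parameters are described in Appendix 5.2 and Appendix 5.3, respectively".

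Appendix 5.2 lists both analytes with the unit 10^6 cells/L. For neutrophils the bands start at "Grade 1: $< \text{LLN} - 1.5 \times 10^6/\text{L", pass through "Grade 3: $< 1.0 - 0.5 \times 10^6/\text{L" and end at "Grade 4: $< 0.5 \times 10^6/\text{L". For lymphocytes they start at "Grade 1: $< \text{LLN} - 0.8 \times 10^6/\text{L" and end at "Grade 4: $< 0.2 \times 10^6/\text{L". The white cell row of the same appendix is on a different scale, with "Grade 4: $< 1.0 \times 10^9/\text{L".

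Appendix 5.1 uses 10^6 cells/L for the same two analytes and gives standard normal ranges of 3000–5800 (neutrophils) and 1500–3000 (lymphocytes), displayed as whole numbers.

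The protocol states neutrophil counts in 10^9/L. The eligibility limit is at least 1.5 × 10^9/L (section 6.1), and the febrile neutropenia criterion is a count below 1.0 × 10^9/L (section 8.2.1.2).

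**The concern.** The numerals 1.5/1.0/0.5 and 0.8/0.5/0.2 are plausible on a 10^9/L scale but not on the 10^6/L scale printed beside them. It appears that the unit was changed to 10^6 without rescaling the limits.

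If the appendix is coded literally, Grade 1 takes in nearly every count below the lower limit of normal, and almost nothing can reach Grade 2. The error runs one way, toward understating toxicity. It would reach Table 14.4.10.1 (abnormal hematology values by CTCAE grade), Table 14.4.12.1 (hematology shifts by CTCAE grade) and the grades in Listing 16.2.3.11. Protocol 4.1.1.1 names neutropenia among the more frequent hematologic abnormalities with entinostat. Protocol 11.2.1 says laboratory abnormalities without clinical significance should in general not be recorded as adverse events. For such counts the laboratory-grade tables are the systematic record.

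**Working it through.** **Inputs.** Limits and units come from SAP Appendix 5.2, normal ranges from SAP Appendix 5.1, and neutrophil thresholds from protocol 6.1 and 8.2.1.2. The lower limit of normal (LLN) is taken as the lower end of the Appendix 5.1 range: 3000 and 1500 × 10^6/L. That is an assumption, because the SAP uses local laboratory limits where available.

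**Unit conversion.** 1 × 10^9/L = 1000 × 10^6/L. The printed neutrophil Grade 4 limit of 0.5 × 10^6/L is 0.5/1000 = 0.0005 × 10^9/L. The printed lymphocyte Grade 4 limit of 0.2 × 10^6/L is 0.0002 × 10^9/L.

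**Against the protocol.** The same numerals appear there on the other scale:
- 1.5 × 10^9 / 1.5 × 10^6 = 1000
- 1.0 × 10^9 / 1.0 × 10^6 = 1000

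**Against the normal ranges.** The ratio of LLN to the floor of Grade 1 shows how wide Grade 1 is:

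| Analyte | As printed | With limits in 10^9/L |
|---|---|---|
| Neutrophils | 3000/1.5 = 2000 | 3000/1500 = 2.0 |
| Lymphocytes | 1500/0.8 = 1875 | 1500/800 = 1.875 |
| White cells (already 10^9/L) | 3.2/3.0 = 1.07 | unchanged |
| Platelets (already 10^9/L) | 130/75 = 1.73 | unchanged |

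On the 10^9/L scale the two rows fall into line with their neighbours.

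**Against the white cell row.** White cell Grade 4 starts below 1.0 × 10^9/L = 1000 × 10^6/L. Neutrophils are a component of that count, yet their printed Grade 4 limit is 1000/0.5 = 2000 times lower.

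**Grading example counts under each reading.**

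| Count (× 10^9/L) | In × 10^6/L | Grade as printed | Grade with limits in 10^9/L |
|---|---|---|---|
| Neutrophils 1.4 | 1400 | 1 | 2 |
| Neutrophils 0.9 | 900 | 1 | 3 |
| Neutrophils 0.4 | 400 | 1 | 4 |
| Neutrophils 0.01 | 10 | 1 | 4 |
| Neutrophils 0.0014 | 1.4 | 2 | 4 |
| Lymphocytes 0.7 | 700 | 1 | 2 |
| Lymphocytes 0.4 | 400 | 1 | 3 |
| Lymphocytes 0.1 | 100 | 1 | 4 |
| Lymphocytes 0.01 | 10 | 1 | 4 |
| Lymphocytes 0.0007 | 0.7 | 2 | 4 |

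As printed, Grade 2 or higher needs neutrophils below 0.0015 × 10^9/L or lymphocytes below 0.0008 × 10^9/L, whatever the LLN. With counts held as whole numbers in 10^6/L, only 0 (Grade 4) and 1 (Grade 2) leave Grade 1 for neutrophils, and only 0 (Grade 4) for lymphocytes.

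**Text-extraction fault?** Unlikely. The exponent 6 appears in all eight graded bands (two analytes, four grades) and agrees with the unit columns of both appendices.

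**The case against.** The slip itself is hard to dispute; the real argument is about its consequence. SAP 3.10.2 names CTCAE 4.03 as the grading standard and the appendix only transcribes it. Programming specifications are a separate document, and a programmer may notice that a Grade 1 band from 3000 down to 1.5 cannot be right. Nothing in the documents shows that any code follows the printed limits. This stands: the misgrading is conditional on the appendix being followed. It does not excuse the appendix, which is where the SAP sends the programmer for the limits.

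The reach is also limited. Adverse event severity is graded by the investigator. Dose-limiting toxicity, eligibility and dose modification do not draw on Appendix 5.2. Tables based on local normal ranges are unaffected, and raw values are listed, so a low count stays visible even where its grade is wrong. Leukopenia is graded from the white cell row, which does not have the fault. Protocol 4.1.1.1 also says Grade 3–4 hematologic abnormalities are much less prevalent in solid tumors, so few patients may be affected. All of this stands and bounds the harm.

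The evidence is stronger for neutrophils than for lymphocytes. The protocol's 1.5 and 1.0 × 10^9/L confirm the scale for neutrophils, although they are an eligibility limit and a febrile neutropenia criterion, not a grading table. For lymphocytes no second set of limits exists, and the factor is inferred from the normal range and the identical unit pattern.

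**Conclusion.** The concern holds. The printed limits for both analytes are too low by a factor of 1000, and the contradiction lies within the documents themselves. If the appendix is followed, close to 100% of values that belong in Grades 2–4 would be reported as Grade 1; the exceptions are recorded counts at or near zero. The damage is confined to laboratory-derived grades and shifts for these two analytes. The primary endpoint, decision rules, investigator-graded adverse events and patient management are not touched. The number of patients affected cannot be estimated from the documents. Because the specification is wrong as written and biases safety reporting in one direction, it must be corrected before the laboratory tables are relied on.

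**What to change.** In SAP Appendix 5.2, keep the unit and restate the limits as 1500/1000/500 × 10^6/L for neutrophils and 800/500/200 × 10^6/L for lymphocytes. Alternatively, change the unit and exponent together to 10^9/L and keep the numerals. Confirm the corrected rows against CTCAE 4.03. Then test the grading program with counts on each side of every limit for both analytes, and rerun Tables 14.4.10.1 and 14.4.12.1 and Listing 16.2.3.11 if they have already been produced.

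The cost is a two-row edit and a short programming check, with no effect on design, sample size or data collection.

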5.3 CTCAE Toxicity Grades: Chemistry

Analyte	Standard Unit	Directional Change of Interest	Toxicity Grades (CTCAE v4.03)
Hepatic			
Albumin	g/L	Decrease	Grade 0: \geq LLN Grade 1: $<$ LLN – 30 g/L Grade 2: $<$ 30 – 20 g/L Grade 3: $<$ 20 g/L Grade 4: Not defined
Alk Phos	U/L	Increase	Grade 0: \leq ULN Grade 1: $>$ ULN – 2.5 \times ULN Grade 2: $>$ 2.5 – 5.0 \times ULN Grade 3: $>$ 5.0 – 20.0 \times ULN Grade 4: $>$ 20.0 \times ULN
ALT	U/L	Increase	Grade 0: \leq ULN Grade 1: $>$ ULN – 3.0 \times ULN Grade 2: $>$ 3.0 – 5.0 \times ULN Grade 3: $>$ 5.0 – 20.0 \times ULN Grade 4: $>$ 20.0 \times ULN

LLN=lower limit of normal. ULN=upper limit of normal. The LLN and ULN for each analyte will be determined from the normal range of each local laboratory.

CTCAE Toxicity Grades: Chemistry (continued)

Analyte	Standard Unit	Directional Change of Interest	Toxicity Grades (CTCAE v4.03)
Hepatic (continued)			
AST	U/L	Increase	Grade 0: \leq ULN Grade 1: $>$ ULN – $3.0 \times$ ULN Grade 2: $>$ $3.0 - 5.0 \times$ ULN Grade 3: $>$ $5.0 - 20.0 \times$ ULN Grade 4: $>$ $20.0 \times$ ULN
Total Bilirubin	micromol/L	Increase	Grade 0: \leq ULN Grade 1: $>$ ULN – $1.5 \times$ ULN Grade 2: $>$ $1.5 - 3.0 \times$ ULN Grade 3: $>$ $3.0 - 10.0 \times$ ULN Grade 4: $>$ $10.0 \times$ ULN
Renal			
Creatinine	micromol/L	Increase	Grade 0: \leq ULN Grade 1: $>$ ULN – $1.5 \times$ ULN Grade 2: $>$ $1.5 - 3.0 \times$ ULN Grade 3: $>$ $3.0 - 6.0 \times$ ULN Grade 4: $>$ $6.0 \times$ ULN

LLN=lower limit of normal. ULN=upper limit of normal. The LLN and ULN for each analyte will be determined from the normal range of each local laboratory.

CTCAE Toxicity Grades: Chemistry (continued)

Analyte	Standard Unit	Directional Change of Interest	Toxicity Grades (CTCAE v4.03)
Electrolytes			
Sodium	mmol/L	Increase	Grade 0: \leq ULN Grade 1: $>$ ULN – 150 mmol/L Grade 2: $>$ 150 – 155 mmol/L Grade 3: $>$ 155 – 160 mmol/L Grade 4: $>$ 160 mmol/L
		Decrease	Grade 0: \geq LLN Grade 1: $<$ LLN – 130 mmol/L Grade 2: Not defined Grade 3: $<$ 130 – 120 mmol/L Grade 4: $<$ 120 mmol/L
Potassium	mmol/L	Increase	Grade 0: \leq ULN Grade 1: $>$ ULN – 5.5 mmol/L Grade 2: $>$ 5.5 – 6.0 mmol/L Grade 3: $>$ 6.0 – 7.0 mmol/L Grade 4: $>$ 7.0 mmol/L
		Decrease	Grade 0: \geq LLN Grade 1: $<$ LLN – 3.0 mmol/L Grade 2: Not defined Grade 3: $<$ 3.0 – 2.5 mmol/L Grade 4: $<$ 2.5 mmol/L

LLN=lower limit of normal. ULN=upper limit of normal. The LLN and ULN for each analyte will be determined from the normal range of each local laboratory.

CTCAE Toxicity Grades: Chemistry (continued)

Analyte	Standard Unit	Directional Change of Interest	Toxicity Grades (CTCAE v4.03)
Electrolytes (continued)			
Magnesium	mmol/L	Increase	Grade 0: \leq ULN Grade 1: $>$ ULN – 1.23 mmol/L Grade 2: Not defined Grade 3: $>$ 1.23 – 3.30 mmol/L Grade 4: $>$ 3.30 mmol/L
		Decrease	Grade 0: \geq LLN Grade 1: $<$ LLN – 0.5 mmol/L Grade 2: $<$ 0.5 – 0.4 mmol/L Grade 3: $<$ 0.4 – 0.3 mmol/L Grade 4: $<$ 0.3 mmol/L
		Increase	Grade 0: \leq ULN Grade 1: $>$ ULN – 2.9 mmol/L Grade 2: $>$ 2.9 – 3.1 mmol/L Grade 3: $>$ 3.1 – 3.4 mmol/L Grade 4: $>$ 3.4 mmol/L
		Decrease	Grade 0: \geq LLN Grade 1: $<$ LLN – 2.0 mmol/L Grade 2: $<$ 2.0 – 1.75 mmol/L Grade 3: $<$ 1.75 – 1.5 mmol/L Grade 4: $<$ 1.5 mmol/L
Calcium	mmol/L	Increase	Grade 0: \leq ULN Grade 1: $>$ ULN – 2.9 mmol/L Grade 2: $>$ 2.9 – 3.1 mmol/L Grade 3: $>$ 3.1 – 3.4 mmol/L Grade 4: $>$ 3.4 mmol/L
		Decrease	Grade 0: \geq LLN Grade 1: $<$ LLN – 2.0 mmol/L Grade 2: $<$ 2.0 – 1.75 mmol/L Grade 3: $<$ 1.75 – 1.5 mmol/L Grade 4: $<$ 1.5 mmol/L

LLN=lower limit of normal. ULN=upper limit of normal. The LLN and ULN for each analyte will be determined from the normal range of each local laboratory.

CTCAE Toxicity Grades: Chemistry (continued)

Analyte	Standard Unit	Directional Change of Interest	Toxicity Grades (CTCAE v4.03)
Electrolytes (continued)			
Bicarbonate*	mmol/L	Decrease	Grade 0: \geq LLN Grade 1: < LLN – 16.0 mmol/L Grade 2: < 16.0 – 11.0 mmol/L Grade 3: < 11.0 – 8.0 mmol/L Grade 4: < 8.0 mmol/L
Phosphorus	mmol/L	Decrease	Grade 0: \geq LLN Grade 1: < LLN – 0.8 mmol/L Grade 2: < 0.8 – 0.6 mmol/L Grade 3: < 0.6 – 0.3 mmol/L Grade 4: < 0.3 mmol/L
Metabolic			
Glucose	mmol/L	Increase	Grade 0: \leq ULN Grade 1: > ULN – 8.9 mmol/L Grade 2: > 8.9 – 13.9 mmol/L Grade 3: > 13.9 – 27.8 mmol/L Grade 4: > 27.8 mmol/L
		Decrease	Grade 0: \geq LLN Grade 1: < LLN – 3.0 mmol/L Grade 2: < 3.0 – 2.2 mmol/L Grade 3: < 2.2 – 1.7 mmol/L Grade 4: < 1.7 mmol/L

LLN=lower limit of normal. ULN=upper limit of normal. The LLN and ULN for each analyte will be determined from the normal range of each local laboratory.

*Bicarbonate toxicity grade are taken from CTCAE v3.0.

6 Tables, Listings, and Figures

6.1 List of Tables

Table Number	Title
Table 14.1.1	Analysis Populations
Table 14.1.2A	Study Disposition – Phase 1b
Table 14.1.2B	Study Disposition – Phase 2
Table 14.1.3A	Demographics and Baseline Characteristics – Phase 1b
Table 14.1.3B	Demographics & Baseline Characteristics – Phase 2
Table 14.1.4A	NSCLC History – Phase 2 – Cohort 1
Table 14.1.4B	NSCLC History – Phase 2 – Cohort 2
Table 14.1.4C	Melanoma Cancer History – Phase 2 – Cohort 3
Table 14.1.4D	Colorectal Cancer History – Phase 2 – Cohort 4
Table 14.1.5	Prior Surgery – Phase 2
Table 14.1.6	Prior Chemotherapy – Phase 2
Table 14.1.7	Prior Radiation Therapy – Phase 2
Table 14.1.8	Prior PD-1/PD-L1 Therapy – Phase 2
Table 14.1.9	Concomitant Medications – Phase 2
Table 14.2.1.1	Summary Statistics for Entinostat Plasma Concentrations (PK)

Table 14.2.1.2	Summary Statistics for Pembrolizumab Plasma Concentrations (PK)
Table 14.2.2.1	Summary Statistics for Pharmacokinetic Parameters of Entinostat (PK)
Table 14.2.2.2	Summary Statistics for Pharmacokinetic Parameters of Pembrolizumab (PK)
Table 14.3.1.1	Entinostat Dosing – Phase 2
Table 14.3.1.2	Pembrolizumab Dosing – Phase 2
Table 14.3.2.1	Entinostat Dosage Modifications – Phase 2
Table 14.3.2.2	Pembrolizumab Dosage Modifications – Phase 2
Table 14.3.3A	Objective Response Rate (irRECIST) – Phase 2 (FAS)
Table 14.3.3B	Objective Response Rate (irRECIST) – Phase 2 (PP)
Table 14.3.3C	Objective Response Rate (RECIST 1.1) – Phase 2 (FAS)
Table 14.3.3D	Objective Response Rate (RECIST 1.1) – Phase 2 (PP)
Table 14.3.4A	ORR by PD-L1 Expression (irRECIST) – Phase 2 (FAS)
Table 14.3.4B	ORR by visceral disease involvement (irRECIST) -Phase 2 (FAS)
Table 14.3.4C	ORR by baseline LDH (%> ULN) -Phase 2 (FAS)
Table 14.3.4D	ORR by previously treated with ipilimumab and PD-1 (Melanoma cohort only) (irRECIST) – Phase 2 (FAS)
Table 14.3.4E	ORR by previously treated with BRAF/MEK inhibitor (Melanoma cohort only) (irRECIST) – Phase 2 (FAS)

Table 14.3.4F	ORR by baseline non-classical monocytes (cut-off median for NSCLC, but it might change for other cohorts) (irRECIST) – Phase 2 (FAS)
Table 14.3.4G	ORR by NLR (irRECIST) – Phase 2 (FAS)
Table 14.3.4H	ORR by dNLR (irRECIST) – Phase 2 (FAS)
Table 14.3.4I	ORR by smoking status (current smoker, former smoker, never a smoker) (NSCLC cohorts only) (irRECIST) – Phase 2 (FAS)
Table 14.3.5A	PFS by PD-L1 expression (irRECIST) – Phase 2 (FAS)
Table 14.3.5B	PFS by current visceral involvement (irRECIST) – Phase 2 (FAS)
Table 14.3.5C	PFS by baseline LDH (%>ULN) (irRECIST) – Phase 2 (FAS)
Table 14.3.5D	PFS by previously treated with ipilimumab and PD-1 (Melanoma cohort only) (irRECIST) – Phase 2 (FAS)
Table 14.3.5E	PFS by Previously treated with BRAF/MEK inhibitor (Melanoma cohort only) (irRECIST) – Phase 2 (FAS)
Table 14.3.5F	PFS by baseline non-classical monocytes (cut-off median for NSCLC, but it might change for other cohorts) (irRECIST) – Phase 2 (FAS)
Table 14.3.5G	PFS by NLR (irRECIST) – Phase 2 (FAS)
Table 14.3.5H	PFS by dNLR (irRECIST) – Phase 2 (FAS)
Table 14.3.5I	PFS by smoking status (current smoker, former smoker, never a smoker) (NSCLC cohorts only) (irRECIST) – Phase 2 (FAS)
Table 14.3.6	Clinical Benefit Rate (irRECIST) – Phase 2 (FAS) (RECIST 1.1) – Phase 2 (FAS)
Table 14.3.7A	PFS status at 6 months (irRECIST) - Phase 2 (FAS)

Table 14.3.7B	PFS status at 6 months – (RECIST 1.1) – Phase 2 (FAS)
Table 14.3.8A	PFS (irRECIST) - Phase 2 (FAS)
Table 14.3.8B	PFS (RECIST 1.1) – Phase 2 (FAS)
Table 14.3.9	Overall Survival – Phase 2 (FAS)
Table 14.3.10	Time to Response – Phase 2 (FAS)
Table 14.3.11	Duration of Response – Phase 2 (FAS)
Table 14.4.1	Overall Treatment-Emergent Adverse Event Information - Phase 2 (Safety)
Table 14.4.1.1	Dose Limiting Toxicities – Phase 1b (Safety)
Table 14.4.1.2	Treatment-Emergent Adverse Events by System Organ Class and Preferred Term -Phase 1b (Safety)
Table 14.4.2	Treatment-Emergent Adverse Events by System Organ Class and Preferred Term - Phase 2 (Safety)
Table 14.4.3	Treatment-Emergent Adverse Events by Preferred Term and Maximum Severity – Phase 2 (Safety)
Table 14.4.4.1	Treatment-Emergent Adverse Events by Preferred Term and Relationship to Any Study Drug – Phase 1b (Safety)
Table 14.4.4.2	Treatment-Emergent Adverse Events by Preferred Term and Relationship to Any Study Drug – Phase 2 (Safety)
Table 14.4.4.3	Treatment-Emergent Adverse Events by Preferred Term and Relationship to Entinostat Alone – Phase 2 (Safety)

Table 14.4.4.4	Treatment-Emergent Adverse Events by Preferred Term and Relationship to Pembrolizumab Alone – Phase 2 (Safety)
Table 14.4.5.1	Treatment-Emergent Adverse Events with Severity of Grade 3 or Greater – Phase 2 (Safety)
Table 14.4.5.2A	Treatment-Emergent Adverse Events with Severity of Grade 3 or Greater and Judged Related to Any Study Drug – Phase 2 (Safety)
Table 14.4.5.2B	Treatment-Emergent Adverse Events with Severity of Grade 3 or Greater and Judged Related to Any Study Drug – Phase 1b
Table 14.4.5.3	Treatment-Emergent Adverse Events with Severity of Grade 3 or Greater and Judged Related to Entinostat – Phase 2 (Safety)
Table 14.4.5.4	Treatment-Emergent Adverse Events with Severity of Grade 3 or Greater and Judged Related to Pembrolizumab – Phase 2 (Safety)
Table 14.4.6.1A	Treatment-Emergent Adverse Events Occasioning Treatment Modification of Any Study Drug – Phase 2 (Safety)
Table 14.4.6.1B	Treatment-Emergent Adverse Events Occasioning Treatment Modification of Any Study Drug – Phase 1b (Safety)
Table 14.4.6.2	Treatment-Emergent Adverse Events Occasioning Treatment Modification of Entinostat Alone – Phase 2 (Safety)

Table 14.4.6.3	Treatment-Emergent Adverse Events Occasioning Treatment Modification of Pembrolizumab Alone – Phase 2 (Safety)
Table 14.4.7.1	Serious Treatment-Emergent Adverse Events by Preferred Term – Phase 2 (Safety)
Table 14.4.7.2	Serious Treatment-Emergent Adverse Events by Preferred Term and Judged Related to Any Study Drug – Phase 2 (Safety)
Table 14.4.7.3	Serious Treatment-Emergent Adverse Events by Preferred Term and Judged Related to Entinostat – Phase 2 (Safety)
Table 14.4.7.4	Serious Treatment-Emergent Adverse Events by Preferred Term and Judged Related to Pembrolizumab – Phase 2 (Safety)
Table 14.4.8.1	Hematology Laboratory Values – Phase 2 (Safety)
Table 14.4.8.2	Chemistry Laboratory Values – Phase 2 (Safety)
Table 14.4.9.1	Abnormal Hematology Laboratory Values According to the Local Laboratory Normal Range – Phase 2 (Safety)
Table 14.4.9.2	Abnormal Chemistry Laboratory Values According to the Local Laboratory Normal Range – Phase 2 (Safety)
Table 14.4.10.1	Abnormal Hematology Laboratory Values by Cycle According to the CTCAE Toxicity Grade – Phase 2 (Safety)
Table 14.4.10.2	Abnormal Chemistry Laboratory Values by Cycle According to the CTCAE Toxicity Grade – Phase 2 (Safety)

Table 14.4.11.1	Hematology Laboratory Value Shifts from Baseline According to the Local Laboratory Normal Range – Phase 2 (Safety)
Table 14.4.11.2	Chemistry Laboratory Value Shifts from Baseline According to the Local Laboratory Normal Range – Phase 2 (Safety)
Table 14.4.12.1	Hematology Laboratory Value Shifts from Baseline According to the CTCAE Toxicity Grade – Phase 2 (Safety)
Table 14.4.12.2	Chemistry Laboratory Value Shifts from Baseline According to the CTCAE Toxicity Grade – Phase 2 (Safety)
Table 14.3.15	Vital Signs – Phase 2 (Safety)
Table 14.3.16	12-Lead Electrocardiogram Normality by Assessment –

